MVA-BN (MVA-BN[®], trade name IMVAMUNE[®] outside the European Union [EU], invented name IMVANEX[®] in the EU) has received marketing authorization in the EU for active immunization against smallpox in adults and in Canada for persons 18 years of age and older who have a contraindication to the first or second generation smallpox vaccines including individuals with immune deficiencies and skin disorders.¹⁰ A Phase 3 clinical study (POX-MVA-013) has been completed (ClinicalTrials.gov Identifier: NCT01144637)⁶. Results of completed and ongoing clinical studies of MVA-BN-based vaccines in more than 8,100 individuals, including elderly subjects (up to age of 80 years), children and subjects in whom replicating vaccines are contraindicated (eg, individuals with HIV infection or diagnosed with atopic dermatitis), have shown that the platform displays high immunogenicity and a favorable safety profile.¹⁷ Across all clinical studies, no trends for unexpected or serious adverse reactions due to the product were detected.

Safety information was pooled from the first 2 studies of MVA-BN-Filo (VAC52150EBL1001 and VAC52150EBL1002). In general, MVA-BN-Filo has been shown to be well tolerated.¹²

Three fifths of the subjects reported at least one local site reaction (injection site pain, tenderness, warmth, redness, swelling and/or itching) following administration of MVA-BN-Filo; mostly of mild severity. The most common reported local site reaction was pain at the injection site. All the local reactions resolved to normal without any lasting effects.

At least one general symptom was reported in two fifths of the subjects following MVA-BN-Filo administration. The most common general symptoms were fatigue, headache, myalgia (muscle pain) and nausea. All general symptoms were transient and resolved without lasting effects.

Changes in laboratory tests were reported following MVA-BN-Filo administration which included hypokalemia and decreased numbers of neutrophils (neutropenia). Both changes in laboratory tests were seen in similar numbers of participants following MVA-BN-Filo and the dummy (placebo) vaccine. Less frequently, events of decreased hemoglobin levels were reported. The changes in laboratory tests were not associated with any complaints or symptoms.

Extensive nonclinical studies support the safety profile of the MVA-BN strain.^{19,20}

Relevant Safety Information from Ongoing VAC52150 Studies

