4.1. Inclusion Criteria

4.1.1. Inclusion Criteria for Healthy Adult Subjects

Each potential subject must satisfy all of the following criteria to be enrolled in the study.

1. Each subject must sign an ICF indicating that he or she understands the purpose of and procedures required for the study and is willing to participate in the study. In case the subject cannot read or write, the procedures must be explained and informed consent must be witnessed by a literate third party not involved with the conduct of the study.
2. Subject must be a man or woman aged 18 to 70 years of age, inclusive at screening.
3. Subject must be healthy in the investigator's clinical judgment on the basis of medical history, physical examination and vital signs performed at screening.
4. Subject must be healthy on the basis of clinical laboratory tests and ECG (only in subjects >50 years) performed at screening. If the results of the laboratory screening tests and ECG are outside the institutional normal reference ranges, the subject may be included only if the investigator judges the abnormalities or deviations from normal to be not clinically significant or to be appropriate and reasonable for the population under study. This determination must be recorded in the subject's source documents and initialed by the investigator. However, the subject should not be included when hemoglobin is lower than the institutional normal reference range (or below the values in [Attachment 3](#) when that range is not available).

Note: The safety laboratory assessments at screening are to be performed within 28 days prior to the prime vaccination and may be repeated if they fall outside this time window.

Note: In case of menstruation, urinalysis must be postponed but a result should be available before the prime vaccination. All urinalyses should be collected as freshly voided, mid-stream, clean catch samples obtained after proper cleansing.

Note: If laboratory screening tests are out of range and deemed clinically significant, repeat of screening tests is permitted only once using an unscheduled visit during the screening period to assess eligibility.

5. Criterion modified per Amendment 3.
- 5.1 Contraceptive use by women should be consistent with local regulations regarding the use of contraceptive methods for subjects participating in clinical studies.

Before randomization (on Day 1), subjects who were born female must be either:

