| Fatigue/malaise | Minimal symptoms; caused minimal or no interference with work, school or self-care activities | Notable symptoms; required modification in activity or use of medications; did not result in loss of work or cancellation of social activities | Incapacitating symptoms; required bed rest and/or resulted in loss of work or cancellation of social activities |
| Myalgia | Minimal symptoms; caused minimal or no interference with work, school or self-care activities | Notable symptoms; required modification in activity or use of medications; did not result in loss of work or cancellation of social activities | Incapacitating symptoms; required bed rest and/or resulted in loss of work or cancellation of social activities |

³ In addition to grading the measured local reaction at the greatest single diameter, the measurement should be recorded as a continuous variable.

⁴ Induration/swelling should be evaluated and graded using the functional scale as well as the actual measurement.

| | | | |
|------------|---|--|---|
| Arthralgia | Minimal symptoms; caused minimal or no interference with work, school or self-care activities | Notable symptoms; required modification in activity or use of medications; did not result in loss of work or cancellation of social activities | Incapacitating symptoms; required bed rest and/or resulted in loss of work or cancellation of social activities |
| Chills | Minimal symptoms; caused minimal or no interference with work, school or self-care activities | Notable symptoms; required modification in activity or use of medications; did not result in loss of work or cancellation of social activities | Incapacitating symptoms; required bed rest and/or resulted in loss of work or cancellation of social activities |

LABORATORY TOXICITY GRADING

Grading scale used for lab assessments is based on 'FDA's Toxicity Grading Scale for Healthy Adult and Adolescent Volunteers Enrolled in Preventive Vaccine Clinical Trials', but grade 3 and 4 are pooled below, consistent with the 3 scale toxicity grading used throughout the protocol. If a laboratory value falls within the grading as specified below but also within the local laboratory normal limits, the value is considered as normal. For hemoglobin only the change from reference is used for the grading. The FDA table does not include toxicity grading for hematocrit, RBC counts or INR.

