| Blood, Serum, or Plasma Chemistries ⁵ | LO/Hi/N ⁶ | Mild (Grade 1) | Moderate (Grade 2) | Severe (Grade 3) |
|--|----------------------|--|--|-----------------------------------|
| Sodium (mEq/L or mmol/L) | LO | 132-134 | 130-131 | ≤129 |
| | HI | 144-145 | 146-147 | ≥148 |
| Potassium (mEq/L or mmol/L) | LO | 3.5-3.6 | 3.3-3.4 | ≤3.2 |
| | HI | 5.1-5.2 | 5.3-5.4 | ≥5.5 |
| Glucose (mg/dL) | LO | 65-69 | 55-64 | ≤54 |
| | HI ⁷ | 100-110 | 111-125 | >125 |
| | HI ⁸ | 110-125 | 126-200 | >200 |
| Blood urea nitrogen | HI | 23-26 (mg/dL) or 8.3-9.4 (mmol/L) | 27-31 (mg/dL) or 9.5- 11.2 (mmol/L) | >31 (mg/dL) or >11.2 (mmol/L) |
| Creatinine | N | 1.5-1.7 (mg/dL) or 133-151 (μmol/L) | 1.8-2.0 (mg/dL) or 152-177 (μmol/L) | >2.0 (mg/dL) or > 177 (μmol/L) |
| Calcium (mg/dL) | LO | 8.0-8.4 | 7.5-7.9 | <7.5 |
| | HI | 10.5-11.0 | 11.1-11.5 | >11.5 |
| Magnesium (mg/dL) | LO | 1.3-1.5 | 1.1-1.2 | <1.1 |
| Phosphorus (mg/dL) | LO | 2.3-2.5 | 2.0-2.2 | <2.0 |
| CK (mg/dL) | N | 1.25-1.5 x ULN | 1.6-3.0 x ULN | ≥3.1 x ULN |
| Albumin (g/dL) | LO | 2.8-3.1 | 2.5-2.7 | <2.5 |

⁵ Depending upon the laboratory used, reference ranges, eligibility ranges and grading may be split out by sex and/or age.

⁶ Low, High, Not Graded.

⁷ Fasting.

⁸ Non-fasting.

| | | | | |
|--|----|----------------|----------------|------------|
| Total protein (g/dL) | LO | 5.5-6.0 | 5.0-5.4 | <5.0 |
| Alkaline phosphatase (U/L) | N | 1.1-2 x ULN | 2.1-3 x ULN | >3 x ULN |
| AST (U/L) | HI | 1.1-2.5 x ULN | 2.6-5 x ULN | >5 x ULN |
| ALT (U/L) | HI | 1.1-2.5 x ULN | 2.6-5 x ULN | >5 x ULN |
| Bilirubin, serum total (mg/dL) – when accompanied by any increase in Liver Function Test | | 1.1–1.25 x ULN | 1.2 –1.5 x ULN | >1.5 x ULN |
| Bilirubin, serum total (mg/dL) – when Liver Function Test is normal | | 1.1–1.5 x ULN | 1.6–2.0 x ULN | >2.0 x ULN |
| Amylase (U/L) | N | 1.1-1.5 x ULN | 1.6-2.0 x ULN | >2.0 x ULN |
| Lipase (U/L) | N | 1.1-1.5 x ULN | 1.6-2.0 x ULN | >2.0 x ULN |

| Hematology | LO/HI/N⁹ | Mild (Grade 1) | Moderate (Grade 2) | Severe (Grade 3) |
|--|----------------------------|-----------------------|---------------------------|-------------------------|
| Hemoglobin (women) change from baseline (g/dL) | LO | Any decrease-1.5 | 1.6-2.0 | >2.0 |
| Hemoglobin (men) change from baseline (g/dL) | LO | Any decrease-1.5 | 1.6-2.0 | >2.0 |
| White blood cell count (cell/mm ³) | HI | 10,800-15,000 | 15,001-20,000 | >20,000 |
| | LO | 2,500-3,500 | 1,500-2,499 | <1,500 |

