7.3.1. Definitions

In determining toxicity grades, the following rules will be applied:

- Worst grades/abnormalities are determined over the entire period (eg, Post-dose 1 or Post-dose 2) separately, including all post-baseline measurements of the corresponding period.
- The abnormalities “abnormally low” and “abnormally high” are considered equally important and both abnormalities are shown in the tables. (This means that the sum of the percentages can exceed 100%).
- If a laboratory value falls within the grading as specified in the grading table but also within the local laboratory normal limits, the value is considered as normal or Grade 0.
- Laboratory results falling between the grading scales will be allocated to the adjacent worst-case grade (because the scale for some parameters in the grading table is not continuous as there may be zones where toxicity grade definitions do not exist).

An abnormality (toxicity grade or abnormality based on normal ranges) will be considered as following vaccination in a period and/or phase if it is worse than the corresponding baseline record. If the baseline value is missing, the abnormality is always considered as following vaccination. A shift from “abnormally low” at baseline to “abnormally high” post-baseline (or vice versa) is also considered as an abnormality following vaccination.

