Fatigue/malaise	Minimal symptoms; caused minimal or no interference with work, school or self-care activities	Notable symptoms; required modification in activity or use of medications; did not result in loss of work or cancellation of social activities	Incapacitating symptoms; required bed rest and/or resulted in loss of work or cancellation of social activities
Myalgia	Minimal symptoms; caused minimal or no interference with work, school or self-care activities	Notable symptoms; required modification in activity or use of medications; did not result in loss of work or cancellation of social activities	Incapacitating symptoms; required bed rest and/or resulted in loss of work or cancellation of social activities

^a In addition to grading the measured local reaction at the greatest single diameter, the measurement should be recorded as a continuous variable.

^b Induration/swelling should be evaluated and graded using the functional scale as well as the actual measurement.

Arthralgia	Minimal symptoms; caused minimal or no interference with work, school or self-care activities	Notable symptoms; required modification in activity or use of medications; did not result in loss of work or cancellation of social activities	Incapacitating symptoms; required bed rest and/or resulted in loss of work or cancellation of social activities
Reactogenicity	Grade 1	Grade 2	Grade 3
Chills	Minimal symptoms; caused minimal or no interference with work, school or self-care activities	Notable symptoms; required modification in activity or use of medications; did not result in loss of work or cancellation of social activities	Incapacitating symptoms; required bed rest and/or resulted in loss of work or cancellation of social activities

LABORATORY TOXICITY GRADING

Grading scale used for lab assessments is based on ‘FDA’s Toxicity Grading Scale for Healthy Adult and Adolescent Volunteers Enrolled in Preventive Vaccine Clinical Trials’, but grade 3 and 4 are pooled below, consistent with the 3 scale toxicity grading used throughout the protocol. If a laboratory value falls within the grading as specified below but also within the local laboratory normal limits, the value is considered as normal. For hemoglobin only the change from reference is used for the grading. The FDA table does not include toxicity grading for hematocrit, RBC counts or INR.

Blood, Serum, or Plasma Chemistries^a	LO/HI/N^b	Mild (Grade 1)	Moderate (Grade 2)	Severe (Grade 3)

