Sodium (mEq/L or mmol/L)	LO	132-134	130-131	≤129
	HI	144-145	146-147	≥148
Potassium (mEq/L or mmol/L)	LO	3.5-3.6	3.3-3.4	≤3.2
	HI	5.1-5.2	5.3-5.4	≥5.5
Glucose (mg/dL)	LO	65-69	55-64	≤54
	HI ^c	100-110	111-125	>125
	HI ^d	110-125	126-200	>200
Blood urea nitrogen	HI	23-26 (mg/dL)	27-31 (mg/dL)	>31 (mg/dL)
Creatinine	HI	1.5-1.7 (mg/dL)	1.8-2.0 (mg/dL)	>2.0 (mg/dL)
Calcium (mg/dL)	LO	8.0-8.4	7.5-7.9	<7.5
	HI	10.5-11.0	11.1-11.5	>11.5
Magnesium (mg/dL)	LO	1.3-1.5	1.1-1.2	<1.1
Phosphorus (mg/dL)	LO	2.3-2.5	2.0-2.2	<2.0
CK (mg/dL)	N	1.25-1.5 x ULN	1.6-3.0 x ULN	≥3.1 x ULN
Albumin (g/dL)	LO	2.8-3.1	2.5-2.7	<2.5
Total protein (g/dL)	LO	5.5-6.0	5.0-5.4	<5.0
Alkaline phosphatase (U/L)	N	1.1-2 x ULN	2.1-3 x ULN	>3 x ULN
AST (U/L)	HI	1.1-2.5 x ULN	2.6-5 x ULN	>5 x ULN
ALT (U/L)	HI	1.1-2.5 x ULN	2.6-5 x ULN	>5 x ULN
Bilirubin, serum total (mg/dL) – when accompanied by any increase in Liver Function Test		1.1–1.25 x ULN	1.26–1.5 x ULN	>1.5 x ULN
Bilirubin, serum total (mg/dL) – when Liver Function Test is normal		1.1–1.5 x ULN	1.6–2.0 x ULN	>2.0 x ULN
Amylase (U/L)	N	1.1-1.5 x ULN	1.6-2.0 x ULN	>2.0 x ULN
Lipase (U/L)	N	1.1-1.5 x ULN	1.6-2.0 x ULN	>2.0 x ULN
Hematology	LO/HI/N^e	Mild (Grade 1)	Moderate (Grade 2)	Severe (Grade 3)
Hemoglobin (women) change from baseline (g/dL)	LO	Any decrease-1.5	1.6-2.0	>2.0
Hemoglobin (men) change from	LO	Any decrease-	1.6-2.0	>2.0

^a Depending upon the laboratory used, reference ranges, eligibility ranges and grading may be split out by sex and/or age.

^b Low, High, Not Graded.

^c Fasting.

^d Non-fasting.

^e Low, High, Not Graded.

baseline (g/dL)		1.5		
White blood cell count (cell/mm ³)	HI	10,800-15,000	15,001-20,000	>20,000
	LO	2,500-3,500	1,500-2,499	<1,500
Lymphocytes (cell/mm ³)	LO	750-1,000	500-749	< 500
Neutrophils (cell/mm ³)*	LO	1,500-2,000	1,000-1,499	< 1000
Eosinophils (cell/mm ³)	HI	650-1500	1501-5000	> 5000
Platelets (cell/mm ³)	LO	125,000-140,000	100,000-124,999	<100,000
Coagulation				
PT (seconds)	HI	1.0-1.10 x ULN	1.11-1.20 x ULN	>1.20 x ULN
International Normalized Ratio (INR) ^a	HI	1.1-1.5 x ULN	1.6-2.0 x ULN	>2.0 x ULN
PTT or aPTT (seconds)	HI	1.0-1.2 x ULN	1.21-1.4 x ULN	>1.4 x ULN
Fibrinogen (mg/dL)	HI	400-500	501-600	>600
	LO	150-200	125-149	<125
Urine				
Protein (dipstick)	HI	Trace	1+	2+
Glucose (dipstick)	HI	Trace	1+	2+
Blood (microscopic) - red blood cells per high power field (RBC/HPF)	HI	1-10	11-50	>50 and/or gross blood

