4. HEMOGLOBIN CUT-OFF VALUES

Where no institutional normal reference ranges are available for hemoglobin, the following cut-off values are proposed. It is imperative to note that there is no standard accepted normative values for hemoglobin in most African countries and therefore, the following recommendations are based on the review of several published sources and in consultation with the sites involved with the study. In the table below, 'simplified' means that the number of cut-off categories has been reduced to decrease complexity and facilitate understanding about eligibility. Similarly, 'adjusted for safety' means that the references may quote lower average or -2 SD values for hemoglobin but these values are considered to be too low for these subjects.

Group	Value (g/dL)		Reference	Outcome
Adult and HIV+	Male 12.1	Female 9.5	LLN value for local sites in Kenya and Uganda, current values being used in Phase 1	Values kept for consistency
Adolescent 16-18 yrs	Male 12.1	Female 9.5	Robins reference 10.4 g/dL for girls and 12.4 g/dL for boys	Values simplified to correspond to adult cut-offs
Adolescent 11-15 yrs	Male 11.0	Female 9.5	Robins reference 11.0 g/dL for girls and boys	Value adjusted down for boys, no change for girls
Children 6-10 yrs	11.0		Robins reference 10.7 g/dL for girls and boys	Value simplified
Children 2-5 yrs	11.0		Robins reference 10.4 g/dL for girls and boys, LLN value for local lab in Kenya 11.5 g/dL for girls and 14.5 g/dL for boys, Schellenberg reference 8.2-9.3 g/dL average anemic defined as <11.0 g/dL	Value simplified and adjusted for safety to 11.0 g/dL
Children 1-2 yrs	11.0		Schellenberg reference 8.0 g/dL average anemic defined as <11.0 g/dL, DMID toxicity table 11.0 g/dL	Value simplified and adjusted for safety to 11.0 g/dL

Robins E and Blum S. Hematologic Reference Values for African American Children and Adolescents. *American J Hematology*. 2007;82, 611-614.

Schellenberg D, et al. The silent burden of anaemia in Tanzanian children: a community-based study. *Bulletin of the World Health Organization* 2003;81:581-590.

DMID US FDA Guidance document DIVISION OF MICROBIOLOGY AND INFECTIOUS DISEASES (DMID) PEDIATRIC TOXICITY TABLES NOVEMBER 2007

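### The SAP does not say whether the normal-limits rule overrides change-based hemoglobin grades; applied literally, a fall of more than 2.0 g/dL that ends in range is tabulated as Grade 0 instead of Grade 3.

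*SAP*

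**What the plan says.** - **General rule.** SAP 7.3.1 lists rules for determining toxicity grades. One of them resets a value that meets a grade "but also within the local laboratory normal limits, the value is considered as normal or Grade 0". SAP Attachment 3 repeats it in the laboratory preamble: "If a laboratory value falls within the grading as specified below but also within the local laboratory normal limits, the value is considered as normal". Protocol Attachment 2 has the same preamble, so the SAP has not departed from the protocol here.
- **Hemoglobin sentence.** Directly after the override, both preambles add: "For hemoglobin only the change from reference is used for the grading". SAP 7.3.1 does not repeat this sentence.
- **Hemoglobin scale.** The row is headed as a change, for example "Hemoglobin (women) change from baseline (g/dL)". A fall up to 1.5 g/dL is Grade 1, 1.6 to 2.0 is Grade 2 and above 2.0 is Grade 3, for both sexes. The other rows of the laboratory table grade an absolute level or a multiple of the upper limit of normal.
- **Use of the grades.** SAP 7.3.3 tabulates worst abnormalities by schedule and period and singles out Grade 3. It refers to the toxicity tables and to the laboratory's normal ranges, without ranking them.
- **Eligibility and limits.** Inclusion criterion 4 (Protocol 4.1.1) says "the subject should not be included when hemoglobin is lower than the institutional normal reference range". Where no institutional range exists, SAP Attachment 4 gives 12.1 g/dL for men and 9.5 g/dL for women, described as the "LLN value for local sites in Kenya and Uganda, current values being used in Phase 1".

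**The concern.** A normal-limits override suits a parameter graded on level: an in-range value should not be called abnormal because the grading table and the local range differ slightly. It does not suit a grade defined by change, because a large fall can end inside the normal range. Criterion 4 keeps out people with low hemoglobin at screening, so many subjects may have room for such a fall.

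At stake are the hemoglobin rows of the worst-grade tables, and the Grade 3 cells in particular. SAP 7.3.3 plans no summary of hemoglobin change that would show the falls another way. The signal is not hypothetical: on laboratory changes after MVA-BN-Filo, Protocol 1.1 says "Less frequently, events of decreased hemoglobin levels were reported". Two programmers could read the same SAP and produce different Grade 3 counts from the same data.

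**Working it through.** No sample size, power or alpha figure bears on this point. The check is of the grading algorithm.

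**Inputs.** Grades by fall: up to 1.5, 1.6 to 2.0, above 2.0 g/dL (SAP Attachment 3; Protocol Attachment 2). Lower limits: 12.1 (men) and 9.5 (women) g/dL (SAP Attachment 4). These are fallback values; limits for the US site are not given. Results are taken to one decimal, and a value equal to the limit counts as in range.

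**Formula.** Fall = baseline − post-dose value. Under the literal reading, the grade becomes 0 if post-dose value ≥ lower limit. A fall of size d is therefore reset when baseline ≥ lower limit + d.

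**Baselines at which a fall is reset to Grade 0**

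| Fall | Grade on change | Men | Women |
|---|---|---|---|
| 1.6 g/dL | 2 | 12.1 + 1.6 = 13.7 or more | 9.5 + 1.6 = 11.1 or more |
| 2.1 g/dL | 3 | 12.1 + 2.1 = 14.2 or more | 9.5 + 2.1 = 11.6 or more |

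**Examples**

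| Subject | Fall | Change grade only | 7.3.1 applied literally |
|---|---|---|---|
| Woman, 12.0 to 9.6 | 2.4 | Grade 3 | Grade 0 (9.6 ≥ 9.5) |
| Man, 15.0 to 12.2 | 2.8 | Grade 3 | Grade 0 (12.2 ≥ 12.1) |
| Man, 14.1 to 12.0 | 2.1 | Grade 3 | Grade 3 (12.0 < 12.1) |

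**How many subjects have the headroom.** The documents give no baseline hemoglobin distribution, so this step is illustration only. Assume a normal baseline truncated at the lower limit, with mean 14.0 to 15.5 (men) or 12.0 to 13.5 (women) and SD 1.0 to 1.3. The share with baseline ≥ lower limit + d is then:

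- d = 2.1: about 43% to 90% of men and 64% to 97% of women.
- d = 3.0: about 14% to 66% of men and 31% to 84% of women.

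These are shares of subjects in whom such a fall would end in range, not shares of falls that will occur. The ranges are too wide to support any statement about most falls.

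**The two readings.** If the hemoglobin sentence is an exemption, every fall above 2.0 is Grade 3, but a drop of 0.1 g/dL is Grade 1 whatever the level, because that grade starts at any decrease. If the sentence only selects the change scale, the override still follows and the examples above apply. Each reading is tenable, and nothing in SAP 7.3.1 or 7.3.3 chooses between them.

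**The case against.** The strongest reply is that hemoglobin is already exempt. A specific sentence containing the word only, placed straight after a general rule, can naturally be read as removing hemoglobin from that rule. This stands as a possible reading, so it cannot be said that the plan does cancel the hemoglobin grades. It does not settle the matter, because the operative list in 7.3.1 omits the sentence and no precedence is given.

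Four stronger inferences are tempting, and the documents do not support them:

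- **That all falls above 2.0 g/dL vanish.** Only those ending within normal limits would be reset.
- **That most falls vanish, or that any arm difference is hidden.** This needs a baseline distribution that the documents do not give.
- **That every subject starts in range.** Criterion 4 bars only low values at screening. High values judged not clinically significant may enter, and the grading baseline is the last value before dose 1, with hematology redrawn on Day 1.
- **That the worst-grade table is the only group summary in which a fall can appear.** SAP 7.3 notes that clinically relevant changes are recorded as adverse events up to 42 days after dose 2. SAP 7.1.3 tabulates those by preferred term and severity, and 7.3.3 adds a listing of clinically significant findings. Both routes depend on a judgement of relevance or significance, so they mitigate the loss but do not replace a systematic count.

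The background signal should not be overstated either. Protocol 1.1 says the human laboratory changes came without complaints or symptoms, and that the rabbit hemoglobin decreases were transient and not adverse.

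**Conclusion.** The conflict is real and should be resolved before the laboratory tables are produced. SAP 7.3.1 as written, with no hemoglobin exception, sends a fall above 2.0 g/dL that ends in range from Grade 3 to Grade 0. With limits of 12.1 and 9.5 g/dL, this applies to a 2.1 g/dL fall from a baseline of at least 14.2 (men) or 11.6 (women). It would thin or empty cells that the SAP singles out for attention.

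The size of the effect in this trial is unknown. It depends on the reading the programmer takes, on each laboratory's limits and on the baseline distribution; a higher lower limit at the US site would leave fewer falls in range. Falls ending below the limit are unaffected, and those judged clinically relevant are still captured elsewhere.

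The pausing rule in Protocol 9.3.2 refers to Grade 3 laboratory abnormalities, and Protocol Attachment 2 carries the same two sentences. Those sentences must be reconciled. The SAP introduction states that enrolment and follow-up are complete, so the live consequence is the final analysis.

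**What to change.** In the SAP analysis, state in 7.3.1 and in the Attachment 3 preamble that the normal-limits override does not remove hemoglobin Grades 2 and 3, and footnote the falls that ended in range. At minimum, leave the grading alone and add one by-arm table of hemoglobin falls in the categories 1.6 to 2.0 and above 2.0 g/dL, regardless of normal limits.

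The cost is one sentence in two places plus a small programming change, or one extra table. More decreases will be graded in all arms, some of them from study blood draws, which the placebo column helps to separate. If the override is kept for Grade 1, so that trivial drops are not graded, there is a step: an in-range fall of 1.5 g/dL is Grade 0 and one of 1.6 is Grade 2. The table note should say so.

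For the protocol grading that the pausing rule relies on, the only request is that the two preamble sentences in Attachment 2 be reconciled.
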